11.2 Behavioral Intervention(s): (not applicable)

12. STUDY PROCEDURES/EVALUATIONS

12.1 Clinical Evaluations and Procedures

12.1.1 HIV Test

An HIV test will be performed to confirm HIV infection if documentation is not available. Acceptable HIV tests include any FDA approved test that is approved for diagnosing HIV infection, such as Oraquick ADVANCE, OraSure Technologies, Inc., INSTI HIV-1/HIV-2 Antibody Test, bioLytical Laboratories Inc., ARCHITECT HIV Ag/Ab Combo, Abbott Laboratories, etc. Participants will receive a finger prick and a few drops of blood will be tested before enrollment.

12.1.2 Pregnancy Test

If the participant is a woman and can become pregnant, a urine pregnancy test will be performed at screening and will be repeated only if pregnancy is suspected.

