Optional Stool Collection		X						X						X						
Optional Genital Secretion ^d		X				X	X	X				X	X	X				X	X	X
Hematology/Chemistry/Coagulation Panel		X				X	X	X				X	X	X				X	X	X
Immune responses		X	X	X	X	X	X	X	X	X	X	X	X	X	X	X	X	X	X	X
HIV-1 RNA sequencing		X	X	X	X	X	X	X	X	X	X	X	X	X	X	X	X	X	X	X
CD4+ T-cell Count		X	X	X	X	X	X	X	X	X	X	X	X	X	X	X	X	X	X	X
HIV-1 DNA sequencing		X	X	X	X	X	X	X	X	X	X	X	X	X	X	X	X	X	X	X
Archive Plasma		X	X	X	X	X	X	X	X	X	X	X	X	X	X	X	X	X	X	X

- Cycle 1 to begin within 30 days of screening visit
- ± 2 days
- Minimum 6 week washout period between cycles
- Paired blood and optional genital secretion sample will be collected **before** each injection
- Pregnancy Test will be repeated only if pregnancy is suspected.

Study Duration: 240 weeks

[figure not shown]
Study Regimen/Intervention: This is a double blind RCT of two vaccines (Pneumovax®23 and Fluarix® or Fluzone®) plus placebo (sterile saline injection). Study participants will be followed for 28 weeks after enrollment. During this 28-week period, blood samples will be collected on day 0 and five subsequent time points after each injection (days 2, 4, 7, 14 and 30). Optional genital secretion samples will be collected on day zero and on days 14 and 30 after each injection. Optional stool will be collected at day zero. Injections (vaccine or placebo) will be administered 12 weeks apart and in a random order, to minimize a possible bias due to the order of the vaccines.

NOTE: Fluarix® quadravalent vaccine is the flu vaccine of choice for this study. Fluzone® quadravalent vaccine may be substituted for Fluarix® only in the event that Fluarix® is unobtainable from the wholesaler/manufacturer.

Primary Objective: To determine the impact of Pneumococcus and Influenza vaccines on the HIV transcriptional activity in individuals who are virologically suppressed for at least 48 weeks on ART.

Primary Outcome: Average change in level of CD4+ T-cell-associated HIV RNA transcription from baseline to day 7 after each injection.

Figure 1. Study Design and sampling

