9.3. Study Arms

Each subject will take Influenza (Fluarix®, GSK or Fluzone®, Sanofi -Pasteur), Pneumococcal (Pneumovax®23, Merck), and placebo. Randomization will determine the order in which the subjects receive the injections. There are six possible study arms, one for each order in which someone can receive the injections:

Placebo, Flu, Pneumovax

Placebo, Pneumovax, Flu

Flu, Placebo, Pneumovax

Flu, Pneumovax, Placebo

Pneumovax, Placebo, Flu

Pneumovax, Flu, Placebo

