10.1.2 Participant Exclusion Criteria

- 10.1.2.1 Uncontrolled psychiatric condition.
- 10.1.2.2 Under the influence of drug(s) or alcohol at time of screening.
- 10.1.2.3 Any condition that, in the opinion of the investigator, would limit follow-up and adequate consent.
- 10.1.2.4 History of allergic reactions to any of the proposed vaccines or egg allergy.
- 10.1.2.5 History of Gullian Barre syndrome.
- 10.1.2.6 Receiving immunosuppressive medications.
- 10.1.2.7 Pregnancy or lactation.

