11. INTERVENTIONS

11.1 Biomedical Interventions

11.1.1 Regimen

Each study subject will receive one dose each of the following: Pneumovax®23, Fluarix® (or Fluzone®), and placebo (sterile saline solution). These will be administered at the baseline visit (Day 0) of each cycle and will precede 30 days of follow-up. After the 30 days of each cycle, there is a washout period (minimum 6 weeks) before the next cycle begins. Each study drug will be administered as a one time intramuscular injection.

NOTE: Fluarix® quadravalent vaccine is the flu vaccine of choice for this study. Fluzone® quadravalent vaccine may be substituted for Fluarix® only in the event that Fluarix® is unobtainable from the wholesaler/manufacturer.

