12.1.9 Study Vaccine Injection

Participant will be injected with the study drug. Administration of the intramuscular injection will be blinded. Subjects will complete 1 dose each of Influenza Vaccine, Pneumococcus vaccine and placebo injection every 12 weeks in random order.

- Fluarix (or Fluzone), a vaccine used to prevent infection by the Flu (influenza) virus, or
- Pneumovax 23, a vaccine used to prevent pneumococcal disease, or
- Placebo, a non-active saline solution that contains no vaccine.

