12.3.1 Screening

At screening a survey will establish inclusion and exclusion criteria. A screening CRF checklist and a screening survey will be completed by nursing staff. The screening visit will involve a discussion of vaccination history and medical history relevant to the inclusion and exclusion criteria. In addition documentation of plasma HIV-1 RNA and CD4+ T-cell counts will be recorded in the source documents and electronic CRF. A urine pregnancy test will be performed at screening in women who can become pregnant and will be repeated only if pregnancy is suspected.

Written informed consent explained by trained clinical staff will occur before starting screening procedures. The baseline visit (study entry) and administration of the vaccine or vaccine-placebo intervention will be performed within 30 days of the screening visit.

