12.3.4 Follow-up

12.3.4.1: Baseline assessments [Day 0 of each cycle]

(These visits will last about 1.5 hours): At study entry the subject should complete all assessments and clinical evaluations with blood sample for banking. Antibody levels for each tested vaccine, cell-associated HIV RNA levels in blood plasma and HIV DNA levels in PBMC should be measured. An optional genital secretion and an optional stool sample will also be collected at baseline assessments. Refusal to provide genital secretion and/or stool sample will not result in termination from the study.

Placebo or vaccine injections: Will be performed by study nursing personnel based on stratification delivered by study pharmacist at baseline.

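### Pregnancy bars entry and ends participation, but the only scheduled pregnancy test is at screening, up to 30, 114 and 198 days before injections 1, 2 and 3

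*Combined protocol and SAP*

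**What the plan says.** Section 10.1.2 lists the exclusion as "10.1.2.7 Pregnancy or lactation". Under sections 12.3.6 and 14.3, a participant who becomes pregnant has an early termination visit and leaves the study. Section 14.3 gives the reason: the vaccines are given outside the usual schedule, and it is unknown whether this could harm a fetus or affect the risk of passing HIV to the child.

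On testing, section 12.1.2 says that "a urine pregnancy test will be performed at screening and will be repeated only if pregnancy is suspected". The Table 1 row has one mark, under Screening, with the footnote "Pregnancy Test will be repeated only if pregnancy is suspected". Sections 12.2, 12.3.1, 12.3.6 and 14.3 give the same rule.

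On timing, section 12.3.1 says that "administration of the vaccine or vaccine-placebo intervention will be performed within 30 days of the screening visit". Section 12.1.9 sets the spacing: "Subjects will complete 1 dose each of Influenza Vaccine, Pneumococcus vaccine and placebo injection every 12 weeks in random order". Section 11.1.1 gives a lower limit: "After the 30 days of each cycle, there is a washout period (minimum 6 weeks) before the next cycle begins".

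For Day 0 of each cycle, section 12.3.4.1 says "At study entry the subject should complete all assessments and clinical evaluations with blood sample for banking". The items it then names do not include a pregnancy test.

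**The concern.** The hazard the protocol describes arises at the injection. The only scheduled test is at screening, where nothing is injected. No scheduled step on any of the three injection days establishes that a woman is not pregnant, and Table 1 marks the eligibility checklist at Screening only.

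Followed exactly, the plan can therefore inject a woman with an unrecognised early pregnancy. At Week 0 that would be someone the exclusion criterion was meant to keep out. At Weeks 12 and 24 it would be someone the discontinuation rule would have removed had the pregnancy been known. What is at stake is participant safety, not inference.

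**Working it through.** **Inputs**

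- Screening to injection 1: 0 to 30 days (12.3.1; Table 1 footnote).
- Injections at Weeks 0, 12 and 24 (Table 1; 18.7), which are days 0, 84 and 168 from injection 1.
- Minimum spacing: a 30-day cycle plus a 6-week washout (11.1.1), 30 + 42 = 72 days.
- Scheduled pregnancy tests: one, at screening.

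**Check of the calendar against the plan's own figure.** The last visit is 30 days after the Week 24 injection: 168 + 30 = 198 days, and 198 / 7 = 28.3 weeks. The plan states 28 weeks, so the calendar is read correctly. (This 198 runs from injection 1 to the last visit. It equals the longest interval below only because the screening window and the follow-up are both 30 days.)

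**Interval from the only scheduled test to each injection.** Interval = days from screening to injection 1 (0 to 30) + days from injection 1 to that injection.

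| Injection | Nominal 12-week spacing | Minimum washout |
|---|---|---|
| 1 | 0 to 30 | 0 to 30 |
| 2 | 84 to 84 + 30 = 114 | 72 to 72 + 30 = 102 |
| 3 | 168 to 168 + 30 = 198 | 144 to 144 + 30 = 174 |

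No maximum washout is stated, so actual intervals could be longer. Scheduled same-day tests before an injection: 0 of 3.

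**Does the saline period remove the exposure?** Section 9.3 says "There are six possible study arms, one for each order in which someone can receive the injections". The positions of the two active vaccines are:

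| Sequence | Active at injections |
|---|---|
| Placebo, Flu, Pneumovax | 2, 3 |
| Placebo, Pneumovax, Flu | 2, 3 |
| Flu, Placebo, Pneumovax | 1, 3 |
| Flu, Pneumovax, Placebo | 1, 2 |
| Pneumovax, Placebo, Flu | 1, 3 |
| Pneumovax, Flu, Placebo | 1, 2 |

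An active vaccine falls at injection 2 or 3 in 6 of 6 sequences, and at injection 3 in 4 of 6. Anyone who completes the three injections therefore receives at least one active vaccine 84 days or more after the only scheduled test (72 or more with the minimum washout).

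**The case against.** The strongest reply is that this is a deliberate choice, stated the same way throughout, and backed by other safeguards. Section 18.4 requires one contraceptive method, started before the first injection and kept up until 30 days after study drug stops. Sections 14.3 and 18.4 require agreement not to become pregnant. Table 1 has history and physical examination at every Day 0, so suspicion can trigger a test. The vaccines are licensed and recommended for people with HIV, and section 14.3 allows their use in pregnancy when medically indicated. The number of women affected may be very small, and intervals in days are not probabilities of harm.

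Most of this is correct, and it limits the weight of the point. It does not close the gap. Contraception and agreement reduce the chance of pregnancy without confirming its absence. Section 12.1.5 describes the examination as brief and directed at symptoms, and a test on suspicion misses a pregnancy that nobody suspects. The case-report forms are not visible and may include a pregnancy question, but a question has the same limit. The reasons for excluding pregnancy are the protocol's own.

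Three further replies stand in part:

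- The Day 0 list in section 12.3.4.1 is not exhaustive, since it omits other items that Table 1 schedules that day. The evidence that counts is Table 1.
- If screening and the first injection fall on the same day, injection 1 is covered. Injections 2 and 3 are not.
- The contraception rule is missing from the inclusion criteria in 10.1.1, but it binds where it stands in 18.4. That is an editorial matter and carries no weight here.

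**Conclusion.** The concern holds. On the nominal schedule the only scheduled pregnancy test precedes injections 1, 2 and 3 by up to 30, 114 and 198 days, and no injection has a scheduled same-day test. The figures assume the latest permitted screening date and 12-week spacing; with the minimum washout the upper limits are 30, 102 and 174 days.

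No risk per woman or for the trial can be given, because the documents supply neither a pregnancy rate nor a count of women of childbearing potential. The change should be made on safety grounds. It has no bearing on alpha, power or the primary endpoint.

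**What to change.** Schedule the same urine test at each Day 0 (Weeks 0, 12 and 24) for women of childbearing potential, with a negative result recorded before the injection. Amend Table 1 and its pregnancy-test footnote, sections 12.1.2, 12.2, 12.3.1, 12.3.6 and 14.3, and the Day 0 list in 12.3.4.1 (repeated in 15.7). The interval from last test to injection then becomes 0 days for all three injections. Testing on suspicion between injections should stay. The contraception rule could be listed in 10.1.1 in the same amendment as a tidy-up.

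The cost is up to three extra urine tests per eligible woman and a few minutes at visits already planned. The ceiling is 56 x 3 = 168 tests, reached only if every participant could become pregnant. No new visit, staff or invasive procedure is needed. The administrative cost is an amendment, which under section 19.1 needs ethics approval and a registration packet to the DAIDS registration office.

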12.1.3 Medical History and Survey

Participants will be asked about their medical history and will be administered a brief survey of incident illness, which will be recorded on Medical History CRF; See Appendix B.

12.1.4 Vaccination History

Participants will be asked about their vaccination history, specifically, the previous seasonal flu and pneumovax vaccines. A documented or reported pneumovax vaccine will be required at least 12 months prior to the screening visit.

12.1.5 Physical Exam

A brief, symptom-targeted physical exam will be performed and recorded on the Physical History CRF; See Appendix C.

12.1.6 Blood Draw

Approximately 50 mL of blood will be drawn at each visit for the purpose of CD4+ T-cell counts, HIV-1 RNA viral load, HIV genetic testing, and immunologic testing. At baseline, day 14 and day 30 of each cycle, we will collect additional 10mL (60mL total) to perform routine blood chemistry tests, hematology and coagulation (safety tests).

12.1.7 Genital Secretion Collection (optional)

- **For Men:** Men will be asked to provide a semen specimen. In the privacy of their home, or in the privacy of our clinic, they will be asked to give us a semen sample. This will require that they do not have sexual activity for 24 hours prior to the semen collection. They will need to wash their hands and then masturbate using only water or KY jelly as a lubricant and deposit their semen into a plastic container which will be provided to them. If they have collected the specimen at home, they will be asked to bring this container to the clinic within 1 hour after collecting their semen sample. This procedure is optional for participants.
- **For Women:** Women will be asked to self-collect cervical-vaginal secretion swabs. See Appendix D. This procedure is optional for participants.
-

12.1.8 Stool Collection (optional)

Stool specimens will be collected from study participants (See Appendix G) for evaluation of the microbiome composition and its connection to immunologic and viral dynamics. This procedure is optional for participants.

12.1.9 Study Vaccine Injection

Participant will be injected with the study drug. Administration of the intramuscular injection will be blinded. Subjects will complete 1 dose each of Influenza Vaccine, Pneumococcus vaccine and placebo injection every 12 weeks in random order.

- Fluarix (or Fluzone), a vaccine used to prevent infection by the Flu (influenza) virus, or
- Pneumovax 23, a vaccine used to prevent pneumococcal disease, or
- Placebo, a non-active saline solution that contains no vaccine.

12.2 Laboratory Evaluations

All laboratory procedures will be conducted in accordance with Good Clinical Laboratory Practices (GCLP) according to the [DAIDS guidelines](#).

A urine pregnancy test will be performed at screening in women who can become pregnant and will be repeated only if pregnancy is suspected.

A rapid HIV test will be performed if no documentation of previous HIV infection is provided.

Table 3 is a summary table of study assays, methods and time points.

	Measurements	Methods	Sample	Sampled Time-points (Days)
Virologic (Aims 1+2)	Cell-associated HIV RNA levels	(dd)PCR	PBMC (CD4+)	
	HIV DNA levels (pol and 2-LTR)	(dd)PCR	PBMC (CD4+)	0, 2, 4, 7, 14, 30 after each injection
	Cell-free HIV RNA levels	SCA	Blood plasma	
	Cell-associated HIV RNA diversity*	env NGS	PBMC (CD4+)	0 and time point with highest cell associated HIV RNA level after the active vaccination
	Cell-associated HIV DNA diversity*	env NGS	PBMC (CD4+)	
	Replication competent HIV levels*	DNA Inducible RNA assay	PBMC (CD4+)	0 and 30 after each active vaccine
Immunologic	Soluble inflammation markers	ELISA	Blood plasma	0, 2, 4, 7, 14, 30 after each injection

(Aim 3)	Vaccine-specific response	ELISA	Blood plasma	
	Cellular inflammation markers	Flow	PBMC	
	HIV-specific T-cell response	Flow ICC	PBMC	
Incidental stimulation	Microbiome Composition	r16s Sequencing	Stool	Day 0
	HHV quantification	qRT-PCR	GS	0, 14, 30 after each injection
	Incident Illness surveys	Survey	--	

Legend: ddPCR: digital droplet PCR, SCA: single copy assay, PBMC: peripheral blood mononuclear cells, ELISA: enzyme linked immunoassay, Flow: flow cytometry, ICC: intracellular cytokine staining, qRT-PCR: quantitative real time PCR. GS: genital secretion. *The 5 participants with the highest sum levels of cell-associated HIV RNA within the 30 days (five measures) following both active vaccinations will undergo these assessments. These same 5 participants will be used for both of these analyses.

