7.3 Major Hypotheses

(All hypotheses are presented “under the alternative”)

Primary Hypothesis:

On average, participants will have a higher absolute increase in levels of cell-associated HIV RNA transcription in CD4⁺ T-cells seven days after receiving either Pneumococcal or Influenza vaccinations, when compared to seven days after receiving placebo.

Secondary Hypotheses:

- Among the five participants with the largest increases in cell-associated HIV RNA in CD4⁺ T-cells following active vaccination (maximum across all observed time-points), we will deep sequence cell-associated HIV RNA and DNA populations at 0, 2, 4, 7, 14 and 30 days. We hypothesize that active vaccines will *non-selectively* activate cellular transcription of HIV, as evaluated by panmixis tests between sequences of HIV DNA and RNA populations at these sampled timepoints.
- On average, participants will have a greater absolute maximum decrease in levels of total CD4⁺ T-cell-associated HIV DNA measured 2-30 days after receiving either Pneumococcal or Influenza vaccinations, when compared to 2-30 days after receiving placebo.
- Among the five participants with the largest increases in cell-associated HIV RNA in CD4⁺ T-cells following active vaccination (maximum across all observed time-points), we will perform inducible RNA assay. We hypothesize that these five participants will have lower levels of replication competent proviruses 30 days after active vaccination, as compared to their levels of replication competent proviruses sampled before this vaccination.
- Participants will have a greater absolute maximum increase in levels of (a) inflammatory cytokines, (b) T-cell activation and proliferation, (c) HIV-specific immune responses, and (d) vaccine-specific immune responses over the 30 days of observation after receiving either active vaccination, when compared to maximum measures taken over the 30 days of observation after receiving placebo.

- Levels of non-antigen specific immune stimulation (cytokines and general T-cell activation) and vaccine-specific immune responses will be positively associated with increased CD4⁺ T-cell-associated HIV RNA transcription and negatively associated with lower levels of HIV DNA, over the 30 days of observation after receiving either Pneumococcal or Influenza vaccinations.

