8.2.2 Aim 1b

Determine if vaccination selectively or non-selectively activates HIV transcription from HIV DNA populations

8.2.3 Aim 2

Determine if active vaccination influences levels of cell associated HIV DNA or replication competent provirus.

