12.2.3 Total Blood Volume

Participants will have blood drawn at each visit. Approximately 50 or 60 mL of blood will be drawn for the following tests and storage for future research:

- CD4+/CD8+ T-cell Count (3 mL of blood).
- HIV-1 RNA (Viral Load) (6 mL of blood).
- Routine blood chemistry tests, a comprehensive metabolic panel and a complete blood count will be performed to determine overall health at baseline, day 14 and day 30 (we will collect 10 mL of additional blood).
- Blood will be collected for storage (6 mL of blood plasma and all PBMC). Some of the blood will be stored to perform future HIV testing and human genetic testing as well as to assess adherence to ART. Blood will be stored with the usual protectors of identity. The results of these tests will not be shared with the participant since these tests are not used for clinical management of their HIV.

Participants will have approximately 50 or 60 mL of blood drawn at a time with an approximate total of 990 ml (4.5 cups) drawn for this study over the course of 8 months.

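### Replication-competent provirus is assayed only around the active injections, so the hypothesised fall is a pre-post change in five selected people with no placebo comparison

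*Combined protocol and SAP*

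**What the plan says.** Section 8.2.3 (Aim 2) is worded as a question about the effect of vaccination: "Determine if active vaccination influences levels of cell associated HIV DNA or replication competent provirus". Its two halves are handled differently.

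- **Replication-competent provirus.** Table 3 in section 12.2 times the inducible RNA assay at "0 and 30 after each active vaccine". Section 7.3 states: "We hypothesize that these five participants will have lower levels of replication competent proviruses 30 days after active vaccination", and the reference is internal, "as compared to their levels of replication competent proviruses sampled before this vaccination". Endpoint 5 in section 15.2.2 is an average change in the five participants with no placebo term. Section 7.2, which gives the rationale for the assay, names no placebo comparison either.
- **Total HIV DNA.** Table 3 times this at "0, 2, 4, 7, 14, 30 after each injection", placebo included. Sections 7.3 and 15.4 compare the maximum decrease after each active vaccine with that after placebo.

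The five people are picked on RNA measured after active vaccination. Table 3 takes "The 5 participants with the highest sum levels of cell-associated HIV RNA within the 30 days (five measures) following both active vaccinations". Section 7.3 uses a different rule: "Among the five participants with the largest increases in cell-associated HIV RNA in CD4⁺ T-cells following active vaccination".

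Every participant has a placebo cycle (section 9.3), blood is drawn on days 0 and 30 of every cycle (Table 1), and section 12.2.3 says "Blood will be collected for storage (6 mL of blood plasma and all PBMC". No section schedules this assay in the placebo cycle.

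**The concern.** The trial's main strength is that each person serves as their own placebo control. Section 7.1.2 criticises earlier observational work and offers a placebo-controlled design as the remedy. For this endpoint that control is not used. Anything that shifts the assay between day 0 and day 30, whether passage of time, assay drift, or an effect of being injected and seen in clinic, would look the same as a vaccine effect.

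This is the measure that section 7.2 introduces to show whether the immune stimulation affects the reservoir. A fall in these five people would invite a statement about the reservoir that the scheduled data could not support.

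**Working it through.** **1. The plan's own figures, as a check on method.** Section 15.4 gives no SD, effect size or power for the inducible RNA assay. The nearest figure is for the other half of Aim 2: n = 50, SD 75, two-sided alpha 0.05, 80% power, detectable difference 30.3 copies/10^6 PBMC. A paired t-test with the noncentral t distribution gives a detectable standardised difference of 0.4042.

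- 0.4042 × 75 = 30.3 (stated 30.3).
- 0.4042 × 625 = 252.6 (stated 253, primary endpoint).
- The other rows of the HIV DNA table (16.2, 20.2, 24.3, 28.3, 32.3) also reproduce.

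**2. The same function at n = 5.** The detectable difference is 1.68 SD of the paired difference. Power at the 0.404 SD for which the trial is sized is about 11%. If an exact signed-rank test were used (the plan names no test for this endpoint), the smallest two-sided p is 2/2^5 = 0.0625. The result is an estimate with or without placebo samples.

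**3. What the missing control costs.** Write the expected day 30 minus day 0 change as:

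- active cycle: v + d + s
- placebo cycle: d

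Here v is the vaccine effect, d the drift common to all cycles, and s the effect of selecting people on active-cycle RNA. Period effects are left out of this line. The planned analysis estimates v + d + s. The active-minus-placebo contrast estimates v + s, so d cancels and s does not.

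The documents give no value for d, so it is an assumption with a range. Take v = s = 0, one change per person, n = 5, and a two-sided 0.05 paired t-test borrowed from the primary analysis. The probability of a nominally significant fall is the upper tail beyond t(0.975, 4 df) of a noncentral t with noncentrality d√5:

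| Assumed downward drift (SD of the change) | P(significant fall) |
|---|---|
| 0 | 2.5% |
| 0.25 | 6% |
| 0.5 | 14% |
| 1.0 | 40% |
| 1.5 | 71% |

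**4. Direction of the selection effect.** This was simulated with no vaccine effect and 50 people. Assumptions: visit-level correlation between RNA and the assay of 0, 0.3 or 0.6, and visit SD 0.5 or 1.0 times the between-person SD. In units of the between-person SD, the expected active-cycle change was:

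- about 0 to +0.09 under the Table 3 rule (highest sum);
- about 0 to +0.56 under the section 7.3 rule (largest increase);
- about 0 in the placebo cycle under either rule.

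Under these assumptions selection gives no shift or a rise, not a fall.

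**5. Feasibility.** Planned assays: 5 people × 2 cycles × 2 days = 20. Placebo cycle: 5 × 1 × 2 = 10, total 30. The blood volume already covers all three cycles: 3 × (3 × 60 + 3 × 50) = 990 mL, as section 12.2.3 states.

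**The case against.** The strongest reply is that this is a five-person exploratory substudy, and that the main component of Aim 2, total HIV DNA, is placebo-controlled and sized at 50. That stands. It limits the importance of the point, and a reader should not infer that Aim 2 as a whole goes unanswered.

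A reader might also infer that choosing people with extreme RNA builds in a fall by regression to the mean. The documents do not support this. Selection is on cell-associated RNA after active vaccination, not on a high day 0 value of the inducible RNA assay. With zero or positive correlation between the two, the simulated shift is nil or upward. Only a negative correlation, for which the documents give no evidence, would turn it downward.

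Nor does the plan assert that a fall has occurred or will be credited to vaccination. Section 7.3 states a hypothesis and section 7.2 says only that provirus will be assessed.

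Three further objections stand in part:

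- **Drift is assumed, not shown.** Section 15.4 describes a stable average for HIV DNA on suppressive treatment, although that is a different assay. The five can be named only once the active cycles are known, and sections 15.5 and 15.8.2 place unblinding at about 44 to 48 months. The assays will therefore probably be run retrospectively, and running day 0 and day 30 together would reduce drift. Such batching is not stated, and it would not deal with time or visit effects.
- **Placebo samples are not a full cure.** They leave selection on active-cycle RNA. Placebo also follows at least one active vaccine in four of the six sequences in section 9.3, and five selected people cannot balance six sequences.
- **Cell supply is uncertain.** Storage of PBMC is stated, but not what remains after the RNA, DNA and flow assays.

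Finally, section 15.8.2 refers additional analyses to a statistical analysis plan whose text is not in the document reviewed. A placebo comparison there cannot be excluded, but Table 3 as written would not supply the data for it.

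**Conclusion.** The point holds in limited form. For replication-competent provirus the plan provides an uncontrolled pre-post change in five selected participants, while the companion measure under the same aim has a placebo comparison. A fall could not be attributed to vaccination. The possible error depends on a drift that the documents do not give and the scheduled assays cannot estimate: from the nominal 2.5% with no drift to about 71% at an assumed 1.5 SD.

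Placebo-cycle samples would remove common drift and so make the estimate easier to interpret. It would be wrong to infer that they make it unbiased or confirmatory: selection and period effects remain, and 80% power at n = 5 needs about 1.68 SD. Priority is low, because this is one small secondary endpoint and the remedy is cheap.

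**What to change.** **Preferred.** In Table 3, extend the inducible RNA assay to days 0 and 30 after every injection, placebo included, in the same five participants, using stored PBMC where enough CD4+ cells remain. Run each person's samples in one batch with the laboratory masked to cycle, which an active-only set does not allow. In section 7.3 and endpoint 5 of section 15.2.2, define the result as the within-person active-minus-placebo change from day 0 to day 30. Report it as an estimate with an interval, and state that it is not confirmatory and does not correct for selection on active-cycle RNA or for period. The cost is ten more assays (20 to 30), with no new visits or blood, subject to a check of cell stocks.

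**If cells or budget do not allow this.** State in section 7.3 and endpoint 5 that the result is descriptive and supports no claim of a vaccine effect on replication-competent virus. This is a wording change only.

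**In either case, reconcile two ambiguities before unblinding.**

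- The rule for choosing the five: largest increase in section 7.3, highest sum in Table 3, highest levels in section 15.2.2, highest response in section 7.2.
- Whether each person contributes one pre-post pair, as the singular in section 7.3 suggests, or two, as Table 3 implies.
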